## **6.8           PHARMACOKINETIC ANALYSES**

A Bayesian feedback population pharmacokinetic analysis of olesoxime PK data collected in this open-label study will be performed using NONMEM. Individual olesoxime PK parameters (e.g., CL/F, Vss/F) will be estimated using a posterior Bayes analysis based on a previously developed population PK model. The results will be reported in a document separated from the clinical study report.

## **6.9           EXPOSURE-RESPONSE (EFFICACY, SAFETY, AND BIOMARKERS) EXPLORATORY ANALYSES**

Graphical analyses of the relationship between exposure and response (efficacy, safety, and biomarkers) will be conducted. The efficacy parameter will be the MFM D1+D2 score. The safety parameters will include adverse events, relevant safety labs, and ECG parameters. The biomarkers will be those linked with the disease, such as SMN mRNA, SMN protein, or other biomarkers linked to the disease pathway.

In case a relevant exposure-response relationship is identified, an empirical exposure response model might be developed using a nonlinear mixed effects modeling approach. Classical hierarchical PK-PD models, like linear, Emax, or sigmoidal Emax models, will be used. The possibility of a delay between the time course of exposure and effects will be investigated.

Details of these graphical analyses and mixed-effects modeling analyses will be described and reported in a document separate from the clinical study report.

## **6.10 PATIENT-REPORTED OUTCOME ANALYSES**

For the PedsQL, data will be presented for the core and neuromuscular modules, by total and sub-scores. Within modules data will be pooled across age bands. Data will be presented separately for child/patient report and parent report. *The data will be summarized by the dose being taken at the time of the assessment.* For scoring purposes, scale items are linearly transformed to a 0–100 scale (0 = 100, 1 = 75, 2 = 50, 3 = 25, and 4 = 0) so that higher scores indicate better health-related quality of life. Scale scores are computed as the sum of the items divided by the number of items which were answered. It is recommended that if more than 50% of the items in the scale are missing, the scale score should not be computed.

*For the SMAIS, total scores will be summarized for each assessment time by the dose being taken at the time of the assessment. Each item is scored on a 0-4 scale (with an additional option to indicate that an item is non-applicable), and item scores are summed to create the total score.*

For EQ-5D-5L Index and VAS scores will be calculated for use in economic modeling, and will be reported separately.

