## **PROTOCOL AMENDMENT, VERSION 4: RATIONALE**

Protocol BN29854 has been amended to incorporate a dose increase of olesoxime from 10 mg/kg once daily (QD) to 10 mg/kg twice daily (BID). Changes to the protocol, along with a rationale for each change, are summarized below:

- Background information on spinal muscular atrophy (SMA) and olesoxime has been updated (see Sections 1.1 and 1.2).
- A dose increase of olesoxime from 10 mg/kg QD to 10 mg/kg BID was included based on information from an exploratory population pharmacokinetic (PK)/pharmacodynamic-efficacy analysis using data from Study TRO19622CLEQ1275-1, which suggests that a higher daily dose of olesoxime may potentially increase the benefit of the drug (see Sections 1.2.3, 1.3, 1.4, 3.1, 3.3.1, and 4.2.2.1). The total daily dose in this study will not exceed 2000 mg. Thus, for patients with body weight >100 kg, the administered dose will be 1000 mg BID (see Sections 3.1.1.3 and 4.2.2.1). All patients agreeing to dose increase must have signed informed consent (see Section 4.4.1.1).
- A newly developed scale assessing function-related independence has been introduced as a patient-reported outcome measure: the SMA Independence Scale (SMAIS) (see Sections 2.4, 2.5, 4.4.10, and 6.10).
- Three new exploratory outcome measures have been introduced: Clinical Global Impression of Change (CGI-C), digital biomarker assessment, and Olesoxime Fatigability Survey (OFS) (see Sections 2.6, 3.1.1.4, 3.3.4, 4.4.8.4, 4.4.12, 4.4.13, and 6.12 and Appendix 1).
- Appropriate safety monitoring procedures to assess any potential risk related to the dose increase have been included. These are reflected in two visits: a dose increase visit and a dose increase follow-up safety visit. These visits include predose increase and follow-up steady-state safety blood sampling (see Section 3.1.1.4 and Appendix 1), as well as predose increase and follow-up steady state 24-hour Holter ECG monitoring based on preclinical findings of rare and isolated arrhythmias (see Sections 3.1.1.4 and 4.4.9.1 and Appendix 1).
- As part of the dose increase and dose increase follow-up safety visits, blood samples for PK and biomarker assessments will be taken, which will help to understand the PK and biomarker profile at the steady state of the new dose (see Section 3.1.1.4 and Appendix 1).

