### **1.3 STUDY RATIONALE**

This study is a Phase II trial for SMA patients who participated in previous studies TRO19622CLEQ1275-1 and/or TRO19622CLEQ1115-1. The current study includes collecting retrospective data between last visit of the above mentioned trials and screening period of this study. As the last patient of study TRO19622CLEQ1275-1 received the last dose in October 2013, the retrospective data collection will serve to understand the disease course of SMA patients after withdrawal of olesoxime treatment for at least 2 years.

The study's main period is an open-label, single arm period in which the patients will receive olesoxime *at the dose of 10 mg/kg BID*, and it will serve to further characterize the safety, tolerability and effectiveness profile of olesoxime in SMA. The outcomes of the study may be compared to natural history data of similar population and outcomes.

*The study was initiated at a dose of 10 mg/kg QD; after Protocol BN29854, Version 4 is in effect, the dose will be increased from 10 mg/kg QD to 10 mg/kg BID with the aim of increasing the exposure to olesoxime and thereby increasing a possible therapeutic benefit of olesoxime, while maintaining appropriate safeguards using a thorough clinical safety monitoring plan. The total daily dose in this study will not exceed 2000 mg. For details on the dose increase rationale, see Section 3.3.1.*

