## **2.4 PATIENT-REPORTED OUTCOME OBJECTIVES**

The patient-reported outcome (PRO) objectives for this study are as follows:

- *To explore changes in level of independence and health-related quality of life following treatment with olesoxime*
- *To assess health-related quality of life and conduct economic modeling using the EuroQol 5-Dimension, 5-Level Questionnaire (EQ-5D-5L)*

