#### **Procedure for Continuing in the Study for Patients Who Do Not Consent to Protocol BN29854, Version 4**

*In case a patient does not consent to Protocol BN29854, Version 4, the dose increase and all new assessments and procedures (see the Summary of Changes and [Appendix 1](#)) per Protocol BN29854, Version 4 should not be performed. This includes the 24-hour Holter ECG monitoring as well as blood sampling for safety, PK, and additional biomarker assessments. It also includes all additional outcome measures per Protocol BN29854, Version 4.*

*Non-consenting patients do not need to attend the dose increase safety follow-up visit 4 weeks later, and they will continue to be administered olesoxime at 10 mg/kg QD.*

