For scoring purposes, scale items are linearly transformed to a 0–100 scale (0=100, 1=75, 2=50, 3=25, and 4=0) so that higher scores indicate better health-related quality of life. Scale scores are computed as the sum of the items divided by the number of items which were answered. It is recommended that if more than 50% of the items in the scale are missing, the scale score should not be computed.

- *The SMAIS was developed specifically for SMA in order to assess function-related independence. The SMAIS contains 29 items, assessing the amount of assistance required from another individual to perform daily activities, such as eating or transferring to/from a wheelchair. Each item is scored on a 0–4 scale (with an additional option to indicate that an item is non-applicable). Item scores are summed to create the total score. Lower scores indicate greater dependence on another individual. The SMAIS will be completed by patients aged ≥12 years. The*

*SMAIS will be conducted at all visits including the dose increase visit, with the exception of screening, Visit 2, and Visit 4.*

*The PROs should be completed in the following order (caregivers should also follow this order when completing these questionnaires about the patient):*

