### Schedule of Assessments (cont.)

Notes: All assessments should be performed within 14 days of the scheduled visit, unless otherwise specified. *Laboratory safety samples should preferably be collected first at each visit under fasting conditions.* Following food, the PRO assessments (in the pre-specified order) should be administered first. Then, all other assessment can be performed in the order convenient for the patient and site. *If it is not possible for the patient to perform all assessments during the day, the site may divide the assessments between 2 consecutive days.*

The following assessments may be performed by an HN professional: vital signs, urine pregnancy test, all lab assessments, and IMP dispensation.

- a Screening can be prolonged up to 6 weeks for relevant clinical, administrative, or operational reasons. Results of standard-of-care tests or examinations performed prior to obtaining informed consent and within 7 days prior to Day 1 may be used; such tests do not need to be repeated for screening.
- b *Dose increase visit can be performed either at next scheduled visit or at unscheduled visit (as described in Section 3.1.1.4).*
- c *Procedures should only be performed by patients that consent to Protocol BN29854, Version 4.*
- d Unscheduled visit: If the patient reports new or worsening of symptoms related to the disease or an adverse event, the treating physician can request that the patient come for a clinical visit for further assessment or monitoring. Assessments should be performed as clinically indicated.
- e The open-label treatment period can terminate at any time (please refer to End of Study Section 3.2). When the study is ended for a particular country, a completion visit should occur as soon as possible but no later than 6 weeks after study end. Patients who discontinue study drug prematurely will return to the clinic for a treatment discontinuation visit 28 ( $\pm 5$ ) days after the last dose of study drug. The assessments requested for Visit *N* represent the typical schedule of assessments during a scheduled visit.
- f Required follow-up information will be collected via a phone call. An unscheduled follow-up visit may occur if the treating investigator deems it necessary.

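### SMAIS starts only with Version 4, yet Section 6.10 plans only totals by visit and current dose, so no within-patient change is produced for the independence objective

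*Protocol*

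**What the plan says.** **Entry of the scale.** The Version 4 amendment rationale introduces SMAIS as a new patient-reported measure. Protocol Section 1.3 records that "The study was initiated at a dose of 10 mg/kg QD", and Section 1.2.4 already reports a 12-month analysis of this same study.

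**Who completes it.** In Appendix 1 the SMAIS row carries footnote c: "Procedures should only be performed by patients that consent to Protocol BN29854, Version 4". Section 3.1.1.4 lists what is not done in patients who decline Version 4: "It also includes all additional outcome measures per Protocol BN29854, Version 4". Of the same patients it says that "they will continue to be administered olesoxime at 10 mg/kg QD".

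**When.** Section 4.4.10 says that "SMAIS will be conducted at all visits including the dose increase visit", apart from screening, Visit 2 and Visit 4. Under Section 3.1.1.4, BID dosing begins the day after the Holter monitor is removed. Self-report is for patients aged 12 or over; a caregiver version is sought for all patients.

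**Analysis.** The only SMAIS analysis is in Section 6.10: "total scores will be summarized for each assessment time by the dose being taken at the time of the assessment". The objective in Section 2.4 is "To explore changes in level of independence and health-related quality of life following treatment with olesoxime". Change from baseline is specified for MFM (Section 6.7), FVC (Section 6.12) and PedsQL (SAP 4.4.2.2), but not for SMAIS. The SAP does not mention SMAIS, and its Section 3.1 has every patient on once-daily dosing.

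**The concern.** The objective is about change, but the planned output is a set of cross-sectional means. A patient's later score is never set against his or her own earlier one, although the schedule supplies a suitable pre-BID score.

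The table is also split by current dose, which invites a QD-versus-BID reading. SMA is progressive, the dose increase happens at different times on study, and decliners give no SMAIS data. A difference between the cells can therefore reflect later disease or different patients, and a trend over visits can reflect who had reached each visit when Version 4 took effect. Either could be taken for an effect of the higher dose on independence.

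**Working it through.** The documents give no sample size, effect or precision for SMAIS, so there is no planned figure to reproduce. The check sets out which scores will exist and what the planned table can show.

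**1. Scores available to patients enrolled before Version 4**

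| Patient | Before Version 4 (QD) | Dose increase visit | Later visits |
|---|---|---|---|
| Consents, dose raised | none | one score, still on QD | scores mainly on BID |
| Declines Version 4 (stays on QD) | none | none | none |

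There is no study-baseline value and, on Section 3.1.1.4, no concurrent QD group with SMAIS.

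**2. What a visit row holds.** Section 3.1.1.4 allows the increase at an extra visit or at the next regular one. Suppose patient A has the increase at Visit 6 and patient B had it at Visit 5. In the Visit 6 row, the QD cell is A and the BID cell is B: different patients. In the Visit 7 row both are on BID. Comparing A's QD cell with A's later BID cell compares an earlier with a later time. If the extra visit is tabulated as its own assessment time, its row is all QD and the contrast is again earlier versus later.

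**3. Can dose be separated from time?** Illustrative layout: 4 patients with 4 scores each, the first on QD and the rest on BID. The design matrix has patient effects, categorical time and dose. If adding dose does not raise the rank, dose cannot be estimated apart from time.

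| Time scale | Rank without dose | Rank with dose |
|---|---|---|
| Time since dose increase | 7 | 7 |
| Study visit, all increase at the same visit | 7 | 7 |
| Study visit, staggered increases | 9 | 10 |
| Hypothetical: one patient stays on QD and completes SMAIS | 7 | 8 |

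Aliasing is complete on the first two scales. With staggered increases, dose is separable, but only through a model with patient and visit effects, which is not planned.

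**4. What pairing adds.** If the same n patients fill both cells, mean(BID) − mean(QD) equals the mean within-patient change. The totals table still does not give the standard deviation or confidence interval of that change. When the cells hold different patients, the identity fails.

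**5. How far drift might matter (MFM only; the documents give no SMAIS slope).** Section 3.3.1 gives a placebo slope of −1.05 MFM D1+D2 points a year. Section 1.2.4 gives a decline of more than 2 a year off drug. Over 1 year that is 1.05 to more than 2 points; over 0.5 year it is 1.05 × 0.5 = 0.53 to more than 2 × 0.5 = 1.0. Section 3.3.1 assumes a 2-point gain from the higher exposure. These slopes come from untreated periods and may overstate drift on QD, but drift of that order would not be negligible.

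**6. Visit windows.** If the SAP 4.4 efficacy windows were applied to SMAIS, only the record closest to the target day is kept. Visit 6 has target Day 547 and a window opening on Day 457, so an extra dose increase visit up to 547 − 457 = 90 days earlier shares its window. The on-QD score could then be displaced by the later BID score.

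**The case against.** The strongest reply is that the proposed change score is itself fully confounded with time: step 3 shows this on exactly the scale it would use. That stands. The change table answers the question about change in individual patients, not the question about dose, and must say so.

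Second, the objective concerns change following olesoxime, whereas a change from the dose increase visit starts after QD treatment in this study. That also stands. No analysis can recover a SMAIS baseline that was never collected.

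Third, a reader might infer that every SMAIS score after the first is on BID. The documents do not support that. Section 4.4.1.1 lets patients decline and reconsider, and can be read as separating consent to the assessments from consent to the dose, although Section 3.1.1.4 treats them as one package. A score at the early discontinuation visit, 28 days after the last dose, would be off drug.

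Fourth, a reader might infer a large, quantifiable gain in precision from pairing. Any such figure needs a within-patient correlation that the documents do not give, and a comparison with an unpaired QD/BID contrast that the plan does not specify.

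Finally, Section 6.10 omits change for PedsQL too, and the SAP supplies it, so silence in the protocol may be only a SAP not yet aligned with Version 4. That may well be the cause. But Section 6.10 does state a SMAIS analysis, it is cross-sectional, and nothing in the supplied SAP adds to it.

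**Conclusion.** The point holds in a limited form. For patients enrolled before Version 4 there is no study-baseline SMAIS, and on-QD data are mainly the single score at the dose increase visit. The planned totals give no within-patient change for an objective stated as change, and QD and BID cells differ by time on study or by patient mix.

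This rests on the consent and scheduling text, not on assumed numbers; the rank check illustrates the structure and the MFM slopes only suggest scale. It would soften if Section 4.4.1.1 were applied so that some patients complete SMAIS while staying on QD.

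The tempting stronger conclusion, that a paired change would reveal the effect of the higher dose, is not supported: there is essentially no concurrent QD group with SMAIS. The outcome is exploratory and descriptive, so the consequence is a table that is easily misread and an objective left unanswered. It should be corrected, but it does not threaten the primary safety analysis.

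**What to change.** In Protocol Section 6.10 and in the SAP:

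- Define the SMAIS at the dose increase visit, before the first BID dose, as the reference value, and exempt it from any visit-window rule that could displace it.
- Add a summary of within-patient change from that value, by time since the first BID dose, with N, mean change and 95% CI. Present self-report and caregiver report separately; Section 6.10 states that separation only in its PedsQL paragraph.
- Keep the planned totals table, with N in each cell.
- State that neither the QD/BID cells nor the post-increase change isolates a dose effect, because there is essentially no concurrent QD group with SMAIS and change is confounded with disease progression. State also that the change does not measure change since olesoxime was started in this study.

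The cost is wording and one extra table. No new data are needed, because the reference score is already scheduled. The downside is that patients without a SMAIS at the dose increase visit drop out of the change summary, so their number should be shown.

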## **6.11 CAREGIVER-REPORTED OUTCOME ANALYSES**

For the WPAI:CG, data will be presented for occupational work productivity and activity impairment (employment status; hours missed due to patient caregiving; hours missed due to other reasons; hours actually worked; and two questions that measure the degree to which health problems affected productivity due to caregiving (presenteeism) and regular daily activities). *The data will be summarized by the dose being taken at the time of the assessment.*

For the SF-36, SF-6D health utility values will be calculated. Additionally, the eight domain scores and both component summary scores will be calculated as norm-based T-scores (general population norm mean = 50, SD = 10). The SF-6D and SF-36 scores will be used for economic modeling, and will be reported separately.

## **6.12 EXPLORATORY ANALYSES**

The effect of olesoxime on the disease progression time-course will be investigated by applying model based approaches using, as appropriate, a disease progression model accounting for the time course of disease status with time being a continuous variable. The results will be reported in a document separate from the clinical study report.

Responder rates, where a responder is defined as no worsening from baseline in MFM D1 + D2, will be summarized *by the dose being taken at the time of the assessment.*

Change from baseline in FVC will be summarized *by the dose being taken at the time of the assessment.*

*The CGI-C responses at each assessment visit will be summarized by the dose being taken at the time of the assessment. Clinicians will score patients using the CGI-C based on their impression of change in the patient's global health since baseline.*

*Smartphone sensor data collected as part of the digital biomarker approach will be analyzed. Patient adherence will be evaluated. From the sensor data, features will be developed for each smartphone-based test and correlated with the MFM and other clinical endpoints. Further exploratory analyses may be conducted. The results will be separately reported from the clinical study report.*

For further exploratory analyses, please refer to the SAP for details.

## **6.13 INTERIM ANALYSES**

Interim analyses of the data may be performed in response to information that may emerge during the course of the study, or for submissions to health authorities. Details of the analyses and timing will be documented in the SAP.

## **7. DATA COLLECTION AND MANAGEMENT**

### **7.1 DATA QUALITY ASSURANCE**

The Sponsor will be responsible for data management of this study, including quality checking of the data. Data entered manually will be collected via EDC through use of eCRFs. Sites will be responsible for data entry into the EDC system. In the event of discrepant data, the Sponsor will request data clarification from the sites, which the sites will resolve electronically in the EDC system.

The Sponsor will produce an EDC Study Specification document that describes the quality checking to be performed on the data. Central laboratory data and other electronic data will be sent directly to the Sponsor, using the Sponsor's standard procedures to handle and process the electronic transfer of these data.

eCRFs and correction documentation will be maintained in the EDC system's audit trail. System backups for data stored by the Sponsor and records retention for the study data will be consistent with the Sponsor's standard procedures.

Data from paper PRO questionnaires will be entered into the EDC system by site staff.

## **7.2 ELECTRONIC CASE REPORT FORMS**

eCRFs are to be completed through use of a Sponsor-designated EDC system. Sites will receive training and have access to a manual for appropriate eCRF completion. eCRFs will be submitted electronically to the Sponsor and should be handled in accordance with instructions from the Sponsor.

All eCRFs should be completed by designated, trained site staff. eCRFs should be reviewed and electronically signed and dated by the investigator or a designee.

At the end of the study, the investigator will receive patient data for his or her site in a readable format on a compact disc that must be kept with the study records.

Acknowledgement of receipt of the compact disc is required.

